### **8.1.3 Post Study Treatment Study Follow-up**

In this study, PFS is a secondary endpoint. Post-study treatment follow-up is of critical importance and is essential to preserving participant safety and the integrity of the study. Participants who

discontinue study drug must continue to be followed for collection of outcome follow-up data, as required and in line with [Table 2.-3](#), withdrawal of consent, or conclusion of the study.

## 8.2 Discontinuation from the Study

Participants who request to discontinue study treatment will remain in the study and must continue to be followed for protocol specified follow-up procedures. The only exception to this is when a participant specifically withdraws consent for any further contact with him/her or persons previously authorized by participant to provide this information.

- Participants should notify the investigator of the decision to withdraw consent from future follow-up **in writing**, whenever possible.
- The withdrawal of consent should be explained in detail in the medical records by the investigator, as to whether the withdrawal is from further treatment with study treatment only or also from study procedures and/or post treatment study follow-up, and entered on the appropriate CRF page.
- In the event that vital status (whether the participant is alive or dead) is being measured, publicly available information should be used to determine vital status only as appropriately directed in accordance with local law.
- If the participant withdraws consent for disclosure of future information, the sponsor may retain and continue to use any data collected before such a withdrawal of consent.

## 8.3 Lost to Follow-Up

- All reasonable efforts must be made to locate participants to determine and report their ongoing status. This includes follow-up with persons authorized by the participant.
- Lost to follow-up is defined by the inability to reach the participant after a minimum of **three** documented phone calls, faxes, or emails as well as lack of response by participant to one registered mail letter. All attempts should be documented in the participant's medical records.
- If it is determined that the participant has died, the site will use permissible local methods to obtain date and cause of death.
- If investigator's use of third-party representative to assist in the follow-up portion of the study has been included in the participant's informed consent, then the investigator may use a Sponsor retained third-party representative to assist site staff with obtaining participant's contact information or other public vital status data necessary to complete the follow-up portion of the study.
- The site staff and representative will consult publicly available sources, such as public health registries and databases, in order to obtain updated contact information.
- If after all attempts, the participant remains lost to follow-up, then the last known alive date as determined by the investigator should be reported and documented in the participant's medical records.

## 9. STUDY ASSESSMENTS AND PROCEDURES

- Study procedures and timing are summarized in the Schedule of Activities.
- Protocol waivers or exemptions are not allowed.

- All immediate safety concerns must be discussed with the Sponsor immediately upon occurrence or awareness to determine if the participant should continue or discontinue treatment.
- Adherence to the study design requirements, including those specified in the Schedule of Activities, is essential and required for study conduct.
- All screening evaluations must be completed and reviewed to confirm that potential participants meet all eligibility criteria before randomization. The investigator will maintain a screening log to record details of all participants screened and to confirm eligibility or record reasons for screening failure, as applicable.
- Procedures conducted as part of the participant's routine clinical management (e.g., blood count) and obtained before signing of informed consent may be utilized for screening or baseline purposes provided the procedure meets the protocol-defined criteria and has been performed within the timeframe defined in the Schedule of Activities.

Additional measures, including non-study required laboratory tests, should be performed as clinically indicated or to comply with local regulations. Laboratory toxicities (eg, suspected drug induced liver enzyme evaluations) will be monitored during the follow-up phase via on site/local labs until all study drug related toxicities resolve, return to baseline, or are deemed irreversible.

If a participant shows pulmonary-related signs (hypoxia, fever) or symptoms (eg, dyspnea, cough, fever) consistent with possible pulmonary adverse events, the participant should be immediately evaluated to rule out pulmonary toxicity, according to the suspected pulmonary toxicity management algorithm in the Nivolumab Investigator Brochure.

- Some of the assessments referred to in this section may not be captured as data in the eCRF. They are intended to be used as safety monitoring by the treating physician. Additional testing or assessments may be performed as clinically necessary or where required by institutional or local regulations.

## 9.1 Efficacy Assessments

Study evaluations will take place in accordance with the schedule of activities presented in [Section 2](#) and [Table 9.1.1-1](#) and [Table 9.1.1-2](#).

Chest, abdomen, pelvis and all known or suspected sites of disease should be assessed at all time points.

Disease assessment with CT and/or MRI, as appropriate, will be performed at baseline and every 6 weeks up to 24 weeks, and every 12 weeks thereafter until PD, the completion of follow-up, initiation of new therapy, or participant withdraw from the study. Tumor responses will be assessed by the investigator as defined by RECIST Version 1.1 (see [Appendix 7](#)).

At Screening, MRI of the brain without and with contrast is required for participants with known or suspected brain metastases. Participants with a history of brain metastasis should have surveillance MRI approximately every 12 weeks, or sooner if clinically indicated.

Participants with a history of bone metastasis may have a bone scan, if clinically indicated.

### 9.1.1 **Imaging Assessment for the Study**

Any incidental findings of potential clinical relevance that are not directly associated with the objectives of the protocol should be evaluated and handled by the Study Investigator as per standard medical/clinical judgment.

CT and MRI are an essential part of the work-up to establish recurrence. The following imaging assessments should be performed at pre-specified intervals: CT of the chest, CT or MRI of the abdomen, pelvis, and other known sites of disease

- CT scans should be acquired with slice thickness of 5 mm or less with no intervening gap (continuous)
- Should a participant have a contraindication for CT IV contrast, a non-contrast CT of the chest and a contrast enhanced MRI of the abdomen and pelvis and other sites of disease may be obtained. MRIs should be acquired with slice thickness of 5 mm or less with no gap (continuous).
- Every attempt should be made to image each participant using an identical acquisition protocol on the same scanner for all imaging time points.
- PET alone will not be considered for the disease assessment. Complementary CT and/or MRI or biopsy must be performed in such cases.

Note: Use of CT component of a PET/CT scanner: Combined modality scanning, such as with FDG-PET/CT, is increasingly used in clinical care and is a modality/technology that is in rapid evolution; therefore, the recommendations outlined here may change rather quickly with time. At present, low-dose or attenuation correction CT portions of a combined FDG-PET/CT are of limited use in anatomically-based efficacy assessments, and it is, therefore, suggested that they should not be substituted for dedicated diagnostic contrast enhanced CT scans for anatomically-based RECIST ([Appendix 7](#)) measurements. However, if a site can document that the CT performed as part of a FDG-PET/CT is of identical diagnostic quality to a diagnostic CT (with IV and oral contrast), then the CT portion of the FDG-PET/CT can be used for RECIST 1.1 measurements. Note, however, that the FDG-PET portion of the CT introduces additional data which may bias an investigator if it is not routinely or serially performed.

- Histology or cytological evidence of recurrence should be attempted in all cases except for brain metastases. Cytology and/or histology are mandatory to confirm recurrence in solitary or in equivocal lesions, any new lesions occurring in the kidney, and lymph nodes unless the lesion is too small to biopsy or the risk of biopsy is substantial (eg, inter-aortal node with risk of bleed after biopsy because of close proximity to the aorta and IVC) in which case the recurrence must be confirmed with a repeat scan 4 weeks later.

Study evaluations will take place in accordance with [Table 9.1.1-2](#) and [Appendix 7](#).

Tumor assessments will be completed by the investigator using RECIST (Response Evaluation Criteria in Solid Tumors) 1.1 criteria, see [Appendix 7](#).

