## 3. TUMOR RESPONSE EVALUATION

### 3.1 Evaluation of target lesions

Complete Response (CR): **Disappearance of all target lesions**. Any pathological lymph nodes (whether target or non-target) must have reduction in short axis to <10 mm.

Partial Response (PR): At least a **30% decrease in the sum of diameters of target lesions**, taking as reference the baseline sum diameters.

Progressive Disease (PD): At least a **20% increase in the sum of diameters of target lesions, taking as reference the smallest sum on study** (this includes the baseline sum if that is the smallest on study). In addition to the relative increase of 20%, the sum must also demonstrate an **absolute increase of at least 5 mm**. (*Note*: the appearance of one or more new lesions is also considered progression).

Stable Disease (SD): Neither sufficient shrinkage to qualify for PR nor sufficient increase to qualify for PD, taking as reference the smallest sum diameters while on study.

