## **3.3 New lesions**

The appearance of new malignant lesions denotes disease progression. The finding of a new lesion should be unequivocal: i.e. not attributable to differences in scanning technique, change in imaging modality or findings thought to represent something other than tumor (for example, some ‘new’ bone lesions may be simply healing or flare of pre-existing lesions). This is particularly important when the subject’s baseline lesions show partial or complete response. For example, necrosis of a liver lesion may be reported on a CT scan report as a ‘new’ cystic lesion, which it is not.

A lesion identified on a follow-up study in an anatomical location that was *not* scanned at baseline is considered a new lesion and will indicate disease progression. An example of this is the subject who has visceral disease at baseline and while on study has a CT or MRI brain scan ordered which reveals metastases. The subject’s brain metastases are considered to be evidence of PD even if he/she did not have brain imaging at baseline.

If a new lesion is equivocal, for example because of its small size, continued therapy and follow-up evaluation will clarify if it represents truly new disease. *If repeat scans confirm there is definitely a new lesion, then progression should be declared using the date of the initial scan.*

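### Section 9.1.1 makes tissue confirmation of recurrence mandatory for several lesion types, although Appendix 7 sets progression by imaging and PFS and DOR need no biopsy

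*Protocol*

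**What the plan says.** Section 9.1.1 of the Protocol lists how imaging is to be done and includes a bullet on tissue. The bullet opens with a general request: "Histology or cytological evidence of recurrence should be attempted in all cases except for brain metastases". It then makes tissue compulsory for named lesion types: "Cytology and/or histology are mandatory to confirm recurrence in solitary or in equivocal lesions, any new lesions occurring in the kidney, and lymph nodes". There is an exception, "unless the lesion is too small to biopsy or the risk of biopsy is substantial", and in that case a repeat scan 4 weeks later takes the place of tissue. Earlier in the same section, the sentence that introduces the routine imaging work-up reads "CT and MRI are an essential part of the work-up to establish recurrence".

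Directly after the bullet, Section 9.1.1 sends tumor assessments to RECIST 1.1 in Appendix 7. There, under target lesions, "the appearance of one or more new lesions is also considered progression". For an equivocal new lesion, "continued therapy and follow-up evaluation will clarify if it represents truly new disease". On dating: "If repeat scans confirm there is definitely a new lesion, then progression should be declared using the date of the initial scan". Appendix 7, Section 1.4.2.7, allows cytology or histology to inform a timepoint assessment but does not require it.

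Section 9 adds: "Protocol waivers or exemptions are not allowed".

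**The concern.** The bullet is written around recurrence. Section 6.1 requires measurable disease at entry in all three cohorts, so these participants have disease that responds, stays stable or progresses. The rule does not match the population.

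The tissue requirement also has no counterpart in the endpoints. PFS and DOR are secondary endpoints based on investigator RECIST 1.1 progression or death. A site that reads the bullet as written, and sees that waivers are not allowed, would perform invasive sampling that neither endpoint uses. A site that follows Appendix 7 for an equivocal lesion would depart from Section 9.1.1.

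What is at stake is mainly participant burden and risk, since the bullet itself gives bleeding after biopsy as an example of the hazard. The secondary issue is uncertainty over when progression is declared while mandatory tissue is pending or non-diagnostic.

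**Working it through.** There is no planned figure to reproduce, because the point depends on no sample size, power or event count. The check sets the rules side by side.

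| Situation | Section 9.1.1 bullet | Appendix 7 | PFS and DOR definitions |
|---|---|---|---|
| Equivocal new lesion | Tissue mandatory unless too small or too risky | Continued therapy and follow-up; dated to the initial scan if repeat scans confirm it (3.3) | First documented RECIST progression; no tissue condition |
| New kidney lesion | Tissue mandatory, same exception | An unequivocal new lesion is progression (3.1, 3.3) | Same |
| Solitary lesion or lymph node | Tissue mandatory, same exception | Change in target sum, unequivocal non-target progression, or a new lesion (3.1, 3.2, 3.3) | Same |
| Any other site except brain | Tissue to be attempted | Same imaging rules | Same |
| Disease returning after complete response | Tissue, if the bullet is read narrowly | Objective documentation only (4.3) | Same |

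The endpoint definitions are in Protocol Section 10.3.1 (PFS) and in SAP Sections 4.1.3 and 4.1.4 with Table 4.1.4-1.

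1. **Equivocal lesions.** The conflict is direct: one rule makes tissue mandatory, and the other lets repeat imaging suffice.
2. **Solitary lesions, new kidney lesions and lymph nodes.** The bullet adds a tissue condition that appears neither in Appendix 7 nor in the endpoint definitions.
3. **Confirmation of progression.** The text under Table 9.1.1-2, repeated in Appendix 7 Section 4.1.2, asks for confirmation after at least 4 weeks under its confirmation-scan rule, and only when this is not clinically burdensome. The tissue bullet has no burden exception, only size and substantial risk.
4. **Schedule.** No biopsy at progression is visible in Tables 2.-2 and 2.-3. The public text of these tables is incomplete, so this carries little weight.
5. **Size.** Tissue samples needed to set progression under Appendix 7 and SAP Table 4.1.4-1: 0. Minimum required by the bullet for a qualifying lesion outside the exception: 1. Difference: 1 − 0 = 1 extra sample at least. This assumes that each qualifying lesion triggers its own sample, which the bullet does not spell out.
6. **Dating.** Where Appendix 7 is followed, the progression date does not change. Appendix 7 Section 3.3 gives a date only for a lesion confirmed by repeat scans, so an equivocal lesion settled by tissue has no explicit rule.

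**The case against.** The strongest reply is that the bullet concerns recurrence and never mentions progression. Appendix 7 Section 4.3 names recurrent and progressive disease separately. On that reading the rule would apply rarely, for example when disease returns after complete response, and the extra biopsies would mostly not arise. This does not hold. The bullet belongs to a list that uses recurrence for the routine CT and MRI work-up, and it names new kidney lesions and equivocal lesions, which overlap with new-lesion progression under RECIST. Even after a complete response, it would demand tissue where Appendix 7 asks only for objective documentation.

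A second reply is that Section 9.1.1 points to Appendix 7 straight after the bullet, so the governing rule is already in place. That protects the analysis. It does not cancel the word mandatory for a site deciding whether to biopsy.

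A third is that Appendix 7 does not exclude tissue, and that tissue can help show whether an equivocal lesion is tumor. That is a reason to permit it, not to compel it.

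Several points on the other side do stand:

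- The size and risk exception removes the most hazardous biopsies, and using it needs no waiver.
- Section 6.1 already requires participants to consent to tumor biopsy.
- No count of affected lesions or participants can be given.
- No case is shown in which a progression date actually moves.
- Enrollment is closed and the SAP is a close-out plan, so the remaining benefit is limited.

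**Conclusion.** The concern holds, with medium confidence. Section 9.1.1 contains a mandatory tissue rule that does not fit the cohorts, conflicts with Appendix 7 for equivocal lesions, and goes beyond it for solitary lesions, new kidney lesions and lymph nodes. Its size is at least one avoidable tissue sample per qualifying lesion that is neither too small nor too risky to biopsy. The total is unknown. The conclusion assumes that sites read the bullet as part of the routine work-up, as its place in the section suggests.

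The statistical effect is minor. There is no change to PFS or DOR where Appendix 7 dating is followed, and an unquantified one for an equivocal lesion settled by tissue. The case for changing the text rests on participant burden and on consistent instructions to sites. It should be fixed, but it does not threaten the main results.

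**What to change.** Delete the tissue bullet from Section 9.1.1, or replace it with wording such as: *Biopsy of a new or equivocal lesion is optional, at the investigator's discretion; PD is determined and dated per Appendix 7, and an equivocal lesion later confirmed by scan or tissue is dated to the initial scan.* The last clause closes the open dating case if the bullet is replaced. If the bullet is simply deleted, the clause could go into Appendix 7 Section 3.3. No separate SAP text is needed.

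The cost is a protocol amendment with documented IRB/IEC approval, as Appendix 2 requires. It can be bundled with any other amendment. No procedure is added and some biopsies are avoided. Because enrollment closed on 26-May-2018, only participants still on study benefit.

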**Table 9.1.1-1: Acceptable Imaging Assessment Methods for Different Anatomic Regions**

Anatomic Region	Preferred Method	Alternative Methods
Chest, abdomen, and pelvis Note: Scan must cover lung apices to diaphragm, diaphragm through entire liver, and to below the pubic symphysis	CT with IV contrast	For chest: CT without contrast can be used only if the participant has a clinical contraindication for iodine-based IV contrast (eg, hypersensitivity, renal insufficiency) For abdomen and pelvis: MRI with gadolinium-based IV contrast is the first alternative method if the participant has a clinical contraindication for iodine-based IV contrast CT without contrast can be used as the second alternative method only if the participant has a clinical contraindication for both contrast-enhanced CT and MRI.
Brain	MRI with IV contrast	CT with IV contrast is the first alternative method if IV gadolinium is clinically contraindicated. MRI without contrast can be used as a second alternative method if a participant has clinical contraindications for both contrast-enhanced CT and MRI
Bone	Bone scintigraphy	PET (18F-fluoride NaF or FDG) or 99m Technetium SPECT

Notes:

- 1) CT scans must be performed with slice thickness of  $\leq 5$  mm. The reconstruction interval should be equal to slice thickness to avoid gap.
- 2) The same modality for a given anatomical coverage and the same scanning procedure (most importantly: reconstruction slice thickness, anatomic coverage, use of IV contrast) should be consistent between baseline and all subsequent follow-up scanning. If possible, the same scanner or an equivalent scanners should be used throughout the study.
- 3) For abdomen and pelvis CT scans, oral contrast is recommended as per institutional standards.
- 4) MRI should include both T1 and T2-weighted sequences with T1-weighted both pre- and post-contrast.
- 5) If bone scan shows hotspots indicative of metastases, further investigation with X-ray, CT, or MRI is warranted.
- 6) All scans generated should be exportable in electronic format (DICOM) to enable secure and rapid electronic transmission to the designated central imaging laboratory. No longer required per Revised Protocol 03.

Imaging restrictions and precautions are described in [Section 7.7.2.6](#).

**Table 9.1.1-2: Schedule of Spiral CT/MRI Tumor Assessments for advanced and Metastatic Cohorts**

Tumor Assessment Frequency	Assessment Window
Tumor assessment at screening (within 28 days of first dose), and then every 6 weeks thereafter up to 24 weeks	± 1 week
Tumor assessment at week 24 and beyond will be every 12 weeks until PD.	± 2 weeks

For the 3 advanced metastatic tumor cohorts a baseline tumor assessments will be performed within 28 days prior to the start of treatment. Participants will then be evaluated for tumor response beginning 6 weeks from the date of first dose (± 1 week.), then every 6 weeks (± 1 week.) thereafter up to 24 weeks, then it will be every 12 weeks (+/- 2 weeks) until disease progression is documented, regardless of early treatment discontinuation due to reasons other than PD, or subsequent therapy is initiated (whichever occurs first).

Confirmation Scans are required as follows:

- Verification of Response: Confirmation of PR and/or CR is required after at least 4 weeks to ensure responses identified are not the result of measurement error.
- Verification of Progression: When not clinically burdensome to the participant, confirmation of PD is required after at least 4 weeks to ensure responses identified are not the result of measurement error.

## 9.2 Adverse Events

The definitions of an AE or serious adverse event (SAE) can be found in [Appendix 3](#).

AEs will be reported by the participant (or, when appropriate, by a caregiver, surrogate, or the participant's legally authorized representative).

The investigator and any designees are responsible for detecting, documenting, and reporting events that meet the definition of an AE or SAE and remain responsible for following up AEs that are serious, considered related to the study treatment or the study, or that caused the participant to discontinue before completing the study.

Immune-mediated adverse events are AEs consistent with an immune-mediated mechanism or immune-mediated component for which non-inflammatory etiologies (eg, infection or tumor progression) have been ruled out. IMAEs can include events with an alternate etiology which were exacerbated by the induction of autoimmunity. Information supporting the assessment will be collected on the participant's case report form.

### Contacts for SAE reporting specified in Appendix 3

